We will recruit men and women with opioid use disorder for a single study corresponding to our study aims. Participants will be randomly assigned to a group: Intentional Affect Regulation, Incidental Affect Regulation, or Psychoeducational Control. Participants will receive a brief (20 minute) training in the affect regulation strategy (or control), followed by a stressor during which the participant will apply this strategy. We will measure stress reactivity, defined as affective (self-report of negative affect), peripheral physiological (cortisol and galvanic skin response), and opioid craving responses to laboratory stress induction. These measures will be collected prior to and following the stress induction. In *Aim 1 (Determine the impact of intentional and incidental affect regulation strategies on reactivity to a stressor)*, we will compare groups with respect to stress reactivity. In *Aim 2 (Determine the association between intentional and incidental affect regulation strategies and behavioral distress tolerance)*, we will examine the association between randomized condition and a short-term behavioral outcome, distress tolerance during a stressor. In our secondary aim (*Quantify the impact of self-regulatory deficits on the efficacy of affect regulation strategies*), we will investigate individual differences in self-regulation as a potential predictor of response to behavioral strategies.

A.2. Primary and Secondary Outcome Measures

The primary outcome measure for Aim 1 is self-reported negative affect on the Positive and Negative Affectivity Schedule. Secondary outcomes include: self-reported opioid craving (Opioid Craving Scale), salivary cortisol, and skin conductance response.

The primary outcome for Aim 2 is behavioral distress tolerance, measured using the Computerized Mirror Tracing Persistence Task (time to discontinuation of the task).

A.3. Inclusion/Exclusion Criteria

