The proposed study includes men and women from all ethnic backgrounds. Subjects age 18 years and older will be included in this study. We will not include children under the age of 18. The representation of opioid use disorder in the Alcohol and Drug Abuse Treatment Program (ADATP) at McLean Hospital consists of a majority of male patients (approximately 73%). Because the inclusion of both men and women is needed in this study to ensure that the study aims are addressed in both genders, we plan to over-sample women to obtain an approximately equal representation of men and women in the proposed study. We will maintain recruitment efforts to keep a nearly equal gender mix.

Previous research with this population from the ADATP has consisted of approximately 88% White and 8% Hispanic subjects, roughly consistent with the national data on opioid use disorder prevalence (79% White, 14% Hispanic). Nonetheless, we will continue to increase our efforts to include minority subjects, by publicizing the study in areas in and around Boston with higher minority representation. According to 2008 census figures, 86% of the Massachusetts population was White, 7% Black/African-American, and 7% other minority.

C. Data Management and Analysis

C.1. Data Acquisition and Transmission

Data collected for the proposed study will include: interviewer-administered measures, self-report instruments, computerized behavioral task measures, and peripheral physiological data (salivary cortisol, galvanic skin response). Interviewer-administered and self-report data will be collected using Research Electronic Data Capture (REDCap). Computerized behavioral task data will be collected on an encrypted computer stored in a locked research office. Biological specimens (saliva) will be collect in [name] and stored in a locked freezer in a locked laboratory. These specimens will then be transported by research staff to the external lab for the quantification of cortisol. Specimens will be transported with only unique study code and will not be transported with identifying information.

C.2. Data Entry Methods

Participant data will be directly entered by the participant into REDCap. Any data entry (e.g., medical record data extraction) conducted by a study staff member will be entered directly into the study database and will be double-entered (i.e., entered on 2 separate occasions, and checked for discrepancies) to protect against potential transcription error.

C.3. Data Analysis Plan

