First, descriptive statistics and exploratory graphical techniques will be used to assess the presence of skewness and/or outliers in the data. The quantitative data will be appropriately transformed if necessary. Randomized groups will be compared with respect to baseline demographic and clinical variables using t-tests and chi-square tests; if significant group differences are identified in any variables known to be highly predictive of outcome, these variables will be adjusted for via their inclusion as covariates.

Aim 1. The hypothesis that the intentional and incidental affect regulation manipulations will be associated with lower reactivity to stress relative to a comparison condition will be tested using a series of analyses of covariance (ANCOVA) of post-baseline (stress-reactive) outcomes (negative affect, craving, and cortisol/galvanic skin response) in a model with both the randomized groups and baseline values of these markers as covariates. A formal test of the main hypothesis of interest corresponds to the test of the randomized group effect in the ANCOVA model (i.e., a test of whether the magnitude of adjusted change in stress markers is different among the three randomized groups). Aim 2. The hypothesis that intentional and incidental affect regulation manipulations will be associated with greater behavioral tolerance of a stressor will be tested using an ANOVA with distress tolerance (i.e., time to discontinuation of the task) as the dependent variable. The test of the main hypothesis of interest corresponds to the test of the randomized group effect in the ANOVA model. Contrasts of interest (for Aims 1 and 2) include the comparison between each affect regulation condition and the control. In exploratory analyses, we will investigate the contrast between the two affect regulation conditions, and whether stress reactivity mediates the effect of group in Aim 2. Secondary Aim. We will investigate whether differences in baseline (pre-manipulation) self-regulatory deficits are associated with stress reactivity. The self-regulation measures will be added to the ANCOVA and the tests of interest include the main and interaction (group by self-regulation) effects.

D. Quality Assurance

D.1. Procedures to Ensure Data Validity and Integrity

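### Aim 2: adjustment for a known strong predictor hangs on a baseline significance test; naming one or two covariates in advance, or none, is a cheap improvement

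*Combined protocol and SAP*

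**What the plan says.** Section C.3 (Data Analysis Plan) opens with a baseline comparison: "Randomized groups will be compared with respect to baseline demographic and clinical variables using t-tests and chi-square tests". The rule for further covariates follows: "if significant group differences are identified in any variables known to be highly predictive of outcome, these variables will be adjusted for". Two conditions must both be met: a significant group difference, and prior standing as a strong predictor. The section gives no significance level for the screen, does not say how t-tests apply to three groups, and names no candidate variable.

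The aims start from different models. Aim 1 is an ANCOVA "in a model with both the randomized groups and baseline values of these markers as covariates", so the baseline marker is always included. The Aim 2 hypothesis "will be tested using an ANOVA with distress tolerance (i.e., time to discontinuation of the task) as the dependent variable", and no covariate is listed. Aim 2 has its own primary outcome (section A.2): "The primary outcome for Aim 2 is behavioral distress tolerance, measured using the Computerized Mirror Tracing Persistence Task". The screening rule is therefore the only route by which Aim 2 can be adjusted.

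Section A.4 gives the design: 120 participants, 40 per group, with at least 80% power at f = 0.29 for Aims 1 and 2, alpha 0.05.

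**The concern.** Adjustment gains precision when the covariate is correlated with the outcome, and the baseline test does not measure that. In a randomized trial any significant baseline difference is a chance finding, so the rule lets chance decide whether a variable already accepted as a strong predictor enters the model. Usually it does not.

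Aim 1 loses little, because its baseline marker is fixed. Aim 2 usually stays unadjusted and gives up whatever precision such a variable could offer. The final Aim 2 model is also unknown until the baseline data have been tested.

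**Working it through.** **Inputs from the documents.** N = 120, 40 per group, f = 0.29, alpha 0.05, power at least 80% (A.4); the Aim 2 ANOVA and the screening rule (C.3).

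**Assumptions.** Screening level 0.05. Normal outcome with within-group SD 1. Normal covariate, linearly related to the outcome with correlation ρ. Group means (0, d, d) with d = 0.29 × 3/√2 = 0.615, which gives f = 0.29. The documents give no ρ and describe no baseline run of the mirror-tracing task, so ρ is varied from 0 to 0.5.

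**Step 1: the plan's own figure.** One-way ANOVA, df 2 and 117, noncentrality N f² = 120 × 0.29² = 10.09. Power is 80.9%, and the smallest f detectable with 80% power is 0.287. The stated figure reproduces without any covariate.

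**Step 2: how often the rule adjusts.** Simulated chance that one variable is flagged:
- any of three pairwise t-tests: about 12%, so it is left out in about 88% of trials;
- three-group chi-square test, evenly split binary variable: 5.5%, left out in about 94%;
- one F-test: 5.0%, left out in 95%.

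**Step 3: Aim 2 power at f = 0.29, one covariate** (200,000 replicates; simulation standard error about 0.1 point).

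| ρ | Rule, pairwise t-tests | Rule, F-test | Always adjusted |
|---|---|---|---|
| 0 | 80.8% | 80.9% | 80.6% |
| 0.1 | 80.8% | 80.8% | 80.9% |
| 0.2 | 81.1% | 81.0% | 82.2% |
| 0.3 | 81.4% | 81.2% | 84.3% |
| 0.4 | 81.8% | 81.3% | 87.2% |
| 0.5 | 82.4% | 81.5% | 90.8% |

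The gain over the rule is nil at 0.1, about 1 point at 0.2, about 3 at 0.3 and 8 to 9 at 0.5. With two independent covariates (pairwise screen, 100,000 replicates), rule against always adjusting gives 81.2% v 83.6% at 0.2 each and 81.8% v 87.6% at 0.3 each.

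Closed-form check: replace f by f/√(1−ρ²) with df 2 and 116. At ρ = 0.3, 0.29/0.954 = 0.304, power 84.6%; at ρ = 0.5, 0.29/0.866 = 0.335, power 91.0%. These run slightly above the simulation because the formula ignores chance imbalance in the covariate.

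**Step 4: type I error under the rule, one candidate.** With the pairwise screen: 4.8%, 4.7% and 4.1% at ρ = 0.2, 0.3 and 0.5 (repeat runs at 0.5 gave 3.9% to 4.2%). With the F screen: 4.9%, 4.9% and 4.5%. Always adjusting gives 5.0% to 5.1%. The rule falls below 5% because in unflagged trials the groups are more alike on the covariate than the unadjusted ANOVA assumes.

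**Step 5: cost of a useless covariate (ρ = 0).** One: 80.97% unadjusted v 80.57% adjusted, a loss of 0.4 point. Two: 80.97% v 80.16%, a loss of 0.8 point.

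**The case against.** The strongest reply is that nothing is broken. An unadjusted ANOVA of a randomized comparison is valid, the power statement relies on no covariate, and the rule keeps type I error at or below 5%. This stands, so the point is an efficiency improvement only. A reader might infer that Aim 2 is underpowered; step 1 shows that it is not.

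The second reply is that the gain is hypothetical, since the documents name no strong predictor of mirror-tracing persistence. This also stands. Section C.1 says "Data collected for the proposed study will include: interviewer-administered measures, self-report instruments, computerized behavioral task measures", so candidates may exist, but none is identified. The rule is nevertheless written for variables already accepted as strong predictors, and it is inferior for exactly those.

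A reader might also infer that unnamed candidates let the analyst choose covariates after seeing outcomes and so inflate type I error. The documents do not support that. The rule is confined to predictors already known, most naturally meaning known beforehand, and says that those which qualify will be adjusted for. It does not permit reporting the most favourable of several analyses. What remains is a gap in specification: the candidates are not listed.

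Finally, the outcome is a time to discontinuation, and section C.3 anticipates skewness and transformation. The gains assume a normal outcome and a linear covariate and may not carry over exactly.

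**Conclusion.** The point holds as a cheap improvement to Aim 2. Under the rule a strong predictor is left out in about 88% to 95% of trials, and little of the available precision is recovered: at correlation 0.5, power is about 82% where fixed adjustment gives about 91%. The benefit depends wholly on a predictive variable having been measured before the training. If none was, the precision gain is zero and only the clearer specification remains. The size also rests on the assumed correlations, the 5% screening level and the normal, linear model.

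**What to change.** Delete the test-then-adjust rule from section C.3. Before outcomes are examined, do one of the following for Aim 2:
- name one or two already collected variables that the sponsor judges strongly predictive of distress tolerance, and analyse by ANCOVA including them whatever the balance; or
- state that no covariate will be used.

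The documents do not identify such a variable, so the choice is the sponsor's. Any covariate should be measured before the training, not merely before the stressor, because section A.1 puts the training first: "Participants will receive a brief (20 minute) training in the affect regulation strategy (or control), followed by a stressor". A measure taken between the two could already reflect the intervention.

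Keep the Aim 1 model as group plus the baseline marker. Leave self-regulation to the secondary aim there, where the plan already places it: "The self-regulation measures will be added to the ANCOVA and the tests of interest include the main and interaction". Baseline characteristics can be described by group without p-values. The unadjusted Aim 2 ANOVA can be kept as a sensitivity analysis.

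The cost is SAP wording, with no new data or participants. Each continuous or binary covariate uses one degree of freedom, and one unrelated to the outcome loses about 0.4 power point.

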Inclusion criteria include (1) age 18 years or older, (2) primary diagnosis of opioid use disorder, and (3) ability to read and provide informed consent. Exclusion criteria include (1) major psychiatric or medical condition that would interfere with the ability to complete study procedures (e.g., acute psychosis), (2) current opioid withdrawal (defined as a score ≥ 4 on the Clinical Opiate Withdrawal Scale; Wesson & Ling, 2003), (3) presence of another current substance use disorder at a severity that requires acute treatment (e.g., alcohol detoxification), (4) endocrine disease or current steroid prescription, or (5) opioid-positive urine drug screen or breath alcohol test on the day of enrollment (not including prescribed medications).

A.4. Power Calculation and Sample Size

We conducted a statistical power analysis to estimate the minimum effect size for the primary outcomes that we would be able to detect with 80% power at a significance level of alpha = 0.05. For this study, we aim to recruit a total of 120 participants. A study of 120 subjects (40 randomized to each group) will have power of at least 80% to detect a difference between means in the magnitude of an effect size of $f = 0.29$ for Aims 1 and 2. For Aim 3, in which self-regulation is added to the ANCOVA model, we would have a statistical power of .80 to detect an effect of $f = 0.31$. Thus, for the main study hypotheses, the study is more than adequately powered to detect a moderate effect size or larger.

B. Trial Management

B.1. Participating Enrolling Clinics

McLean Hospital is the performance site for the proposed study. All participant enrollment and data collection will occur in [name] in the Division of Alcohol and Drug Abuse at McLean Hospital.

B.2. Projected Timeline

Months 1-2: hire study staff, pilot tasks; Months 3-21: recruit and enroll participants; Months 22-24: conduct data analysis and manuscript preparation. Data entry and quality assurance will be conducted throughout the study.

B.3. Target Population Distribution

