In addition to the procedures described above, several procedures will be implemented to ensure accuracy and completeness of data. First, in the REDCap database we will use restricted ranges (i.e., rejecting any data point out of the potential range) and forced responses to all questions. This will ensure that we have complete data, with the exception of a participant choosing to discontinue a study prior to completion. Participants will still have the option to decline to answer any question through the availability of a decline to answer checkbox for each question. Second, research assistants or other staff implementing study procedures will be instructed to check the completeness of all data prior to a participant leaving the clinic, consistent with prior studies in [name]. Finally, the dataset will be carefully screened prior to data analysis for out-of-range values and to ensure that any missing data (i.e., declined questions) are labeled accurately and accounted for appropriately in all data analysis.

E. Regulatory Issues

The proposed research will be reviewed and approved by the Partners HealthCare IRB (which covers all Partners HealthCare hospitals, including McLean Hospital). In addition, the PI will have responsibility for continuous monitoring of the data and safety of subjects in the study. Data and safety monitoring will take place continuously throughout the study's duration. We will report adverse events and all serious adverse events that occur during the course of the trial to the Partners HealthCare IRB. At the time of annual, continuing review, we will provide the Partners HealthCare IRB with a summary of any unexpected and related adverse events, as well as any other unanticipated problems that occurred since the last continuing review.

E.1. Reporting Serious Adverse Events (SAEs)

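### Does analysing time to discontinuation by ANOVA shrink the Aim 2 effect and lose power that a survival analysis would keep?

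*Combined protocol and SAP*

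**What the plan says.** Section A.2 makes behavioural distress tolerance the primary outcome for Aim 2. It is scored as the time until the participant stops the Computerized Mirror Tracing Persistence Task. Section C.3 says the Aim 2 hypothesis "will be tested using an ANOVA with distress tolerance (i.e., time to discontinuation of the task) as the dependent variable", and adds: "The test of the main hypothesis of interest corresponds to the test of the randomized group effect in the ANOVA model". Each strategy is then contrasted with control.

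For awkward distributions, C.3 plans descriptive and graphical checks for skewness and outliers, followed by "The quantitative data will be appropriately transformed if necessary". Section D.2 asks that "any missing data (i.e., declined questions) are labeled accurately and accounted for appropriately in all data analysis", which concerns unanswered items and not participants who keep tracing.

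Section A.4 states the power at alpha 0.05 with 120 participants, 40 per group, as the ability "to detect a difference between means in the magnitude of an effect size of $f = 0.29$ for Aims 1 and 2". No section states a maximum task duration, a score for someone who never discontinues, or an expected share of such participants.

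**The concern.** Time to discontinuation is a time to an event, and a supervised laboratory task presumably has to stop at some point. Anyone still working then has a right-censored time, and ANOVA would use the limit as if it were the quitting time. A transformation cannot repair this, because tied values stay tied. If the strategies work, more participants reach the limit in the strategy arms than in control, so the compression falls where benefit is expected.

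The stakes would be real: an Aim 2 mean difference governed by an undisclosed task setting, and a primary test with less power than A.4 suggests. In a simulation with a halved quitting hazard in both strategy arms, ANOVA power falls from 83% without a limit to 54% when 40% of controls reach it. The raw mean difference falls from 1.00 to 0.14 control-mean units.

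**Working it through.** **Inputs.** From A.4: N = 120, three groups of 40, alpha 0.05, power at least 80%, f = 0.29. From C.3: omnibus group test in a one-way ANOVA. Assumed, because the documents give nothing: a common task limit, the share of participants reaching it, and the distribution of quitting times.

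**1. The plan's own figure.** Cohen's f is the SD of the group means divided by the within-group SD. The noncentrality is f² × N = 0.29² × 120 = 10.09, on 2 and 117 degrees of freedom. Power is 0.809, the smallest f detectable with 80% power is 0.287, and 118 participants suffice. The figure reproduces. It is a standardized effect on whatever score is analysed, so it does not presuppose an uncapped score.

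**2. Raw difference against standardized effect.** Take exponential times with control mean 1 and strategy mean 2 (hazard halved), and a limit L reached by a share p of controls.

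- Share of strategy participants at the limit: √p.
- Restricted means: 1 − p for control and 2(1 − √p) for the strategies. The difference is (1 − √p)².
- Second moment of the capped time, with mean θ and S = exp(−L/θ): 2θ²(1 − S) − 2θLS.
- With two equal strategy means, the SD of the three group means is the difference × √2/3.

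No limit: difference 1.00, within-group variance (1 + 4 + 4)/3 = 3, f = 0.471/1.732 = 0.272.

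p = 0.2 (L = 1.609): difference (1 − 0.447)² = 0.306. The variances are 0.956 − 0.640 = 0.316 (control) and 1.543 − 1.222 = 0.321 (strategies), so the within-group SD is 0.565. Then f = 0.306 × 0.471/0.565 = 0.255.

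p = 0.4: difference (1 − 0.632)² = 0.135, within-group SD 0.300, f = 0.135 × 0.471/0.300 = 0.212.

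At p = 0.2 the raw difference has lost 69% of its size, but f only about 6% (0.255/0.272 = 0.94), because the SD shrinks too. Power depends on f. The noncentral F formula gives 69% at f = 0.255 and 53% at f = 0.212, against simulated ANOVA power of 68% and 51%.

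These cases are also heavier than their labels. With 20% and 40% of controls capped, the share of all participants capped is (0.2 + 2 × 0.447)/3 = 36% and (0.4 + 2 × 0.632)/3 = 56%.

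**3. How much of the loss belongs to ANOVA.** Same model, 1,500 simulated trials per cell (Monte Carlo standard error at most √(0.25/1500) = 1.3 points):

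| Controls at limit | ANOVA | Log-rank | Gap |
|---|---|---|---|
| 0% | 83% | 89% | 6 |
| 20% | 68% | 75% | 7 |
| 40% | 54% | 63% | 9 |
| 60% | 34% | 42% | 8 |

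From 0% to 40%, ANOVA loses 29 points and log-rank 26. Six points of the gap exist with no censoring at all, so the limit adds 1 to 3. The ceiling removes information from both tests.

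**4. Dependence on the distribution.** Second simulation: f = 0.29 before capping, limit set by the share of all participants capped, 20,000 trials for ANOVA and 6,000 for log-rank. Entries are ANOVA / log-rank power:

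| All capped | Normal | Exponential | Weibull, shape 2 |
|---|---|---|---|
| 0% | 81 / 75 | 91 / 94 | 85 / 89 |
| 10% | 80 / 75 | 90 / 93 | 82 / 88 |
| 30% | 78 / 74 | 82 / 87 | 69 / 80 |
| 50% | 71 / 71 | 66 / 74 | 52 / 66 |
| 70% | 59 / 63 | 43 / 51 | 32 / 44 |

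With 10% capped, ANOVA loses at most about 3 points. For normal times it leads until about half are capped.

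For lognormal times (log-SD 0.8, log-shift 0.5), with 0/20/40% of controls capped, ANOVA has 63/77/71% power and log-rank 75/75/70%. Here a limit raises ANOVA power, because it trims the long right tail. A separate run gave 78/73% against 75/70% at 20/40%. Exponential and Weibull times with a scale shift are proportional-hazards models, which favour log-rank, so varying the Weibull shape does not test this dependence.

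**5. Validity.** Under the null with exponential times and 0 to 80% capped, ANOVA type I error is 0.046 to 0.050. With one common limit, the capped mean is the restricted mean persistence time, which is a legitimate estimand.

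**The case for a change.** The strongest case for the concern is this. The outcome is an event time, and an open-ended laboratory task is hard to imagine, so some limit is likely. The only stated remedy cannot separate tied values, and for exponential times a log transformation lowers ANOVA power further, to 40% with 40% of controls capped. Where the quitting hazard rises with time, the cost of ANOVA is not trivial: for Weibull shape 2 with half of all participants capped, log-rank leads by 14 points (66% against 52%), of which only about 4 are present without a limit. A survival analysis would use the same data.

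Several parts of this stand. A pile-up at a limit cannot be transformed away, the raw mean difference would depend on the limit, and the plan does not say how a participant who never quits is scored.

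The inference to a defective analysis does not follow. The 14-point figure needs a limit, half the sample reaching it and a favourable hazard shape, and the documents support none of the three. If everyone quits, nothing is censored. The document calls itself a protocol summary, so task settings may simply not be reproduced in it. Section B.2 schedules piloting of the tasks in months 1 and 2, and C.3 begins with graphical checks; both could reveal a ceiling. A hazard ratio also brings a proportional-hazards assumption and answers a slightly different question from mean persistence time.

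**Conclusion.** The concern does not hold. ANOVA on persistence time is a valid test of the Aim 2 hypothesis, with or without a common task limit, and its error rate stays near 5%. The power statement in A.4 is correct as a standardized effect (0.809 at f = 0.29). The claimed shrinkage is in raw units, and most of the claimed power loss would occur under a log-rank test too.

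What remains is a difference in efficiency whose size and sign depend on an unknown distribution. At half of all participants capped, log-rank leads by about 1 to 14 points across the normal, exponential and Weibull cases. It trails for normal times at 40% capped or less, and for the lognormal case at 20% and 40% of controls capped. Choosing Cox over ANOVA as the primary analysis is a matter on which reasonable statisticians would differ.

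All capped-data figures rest on assumed limits and distributions. The task's maximum duration, the score given to participants who never quit and the share at the limit in each arm would help a reader interpret the result. Their absence is missing detail, not an error of analysis.
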